### **5.2. Breaking the Blind**

Treatment assignment will be blinded to the sponsor study team, subject and investigator. At the initiation of the study, the study site will be instructed on the method for breaking the blind. The method will be either a manual or an electronic process. Blinding codes should be broken only in emergency situations for reasons of subject safety. Whenever possible, the investigator or sub-investigator will consult with a member of the study team prior to breaking the blind. When the blinding code is broken, the reason must be fully documented and entered on the case report form (CRF), and the subject is to be discontinued from the study.

### 5.3. Subject Compliance

Investigational product will be administered by the subject in the outpatient setting (each morning, daily for the duration of the treatment period). A dosing diary will be given to the subject with instructions on how to record the blister card being used and also the daily times of investigational product administration. The subject will bring all blister cards, used and un-used, back to the clinic at each visit. At each visit, a tablet count will be done by the research staff, and the subject will be questioned about any missed or extra doses taken. Site personnel will assess administration compliance based on the drug accountability of the blister packs, review of the dosing diary, and discussion with the subject. In cases where tablets are unaccounted for by the dosing diary and/or questioning of subjects, the site will consider the drug accountability to be a source for missed or additional doses. A subject will be considered compliant with the protocol at a study treatment compliance range of 80%-120%.

In cases where the subject is outside the compliance range, a protocol deviation will be captured and the site is expected to take appropriate actions depending on the reason for non-compliance (eg, if a subject did not have a valid reason for not taking investigational product, that the subject is re-educated on investigational product administration requirements and expectation to adhere to the requirements). Cases of repeated non-compliance may result in discontinuation of the subject from the study, if deemed necessary by the investigator and/or sponsor.

### 5.4. Investigational Product Supplies

#### 5.4.1. Dosage Form(s) and Packaging

Blinded PF-06649751 and its matched placebo will be provided as tablets for oral administration. PF-06649751 0.25 mg, 1 mg, 5 mg and their matching placebo will be supplied in blister cards. At each dispensing visit, subjects will receive sufficient quantity of investigational product to last until their next scheduled visit. Each blister card will be labeled according to local regulatory requirements.

#### 5.4.2. Preparation and Dispensing

The PF-06649751 0.25 mg, 1 mg, 5 mg tablets, and matching placebo are to be dispensed using a drug management system at each visit. A qualified staff member will dispense the investigational product via unique container numbers in the blister card(s) provided per the study visit schedule. The subject/caregiver are to be instructed to maintain the product in the blister cards provided throughout the course of dosing and return all blister cards, used and unused, to the site at the next study visit for accountability.

### 5.5. Administration

For investigational product administration, subjects (and caregivers, as applicable) should be instructed as follows:

- Take 3 tablets at approximately the same time each morning.

- Swallow each tablet whole, with water.
- Do not manipulate or chew the tablet prior to swallowing.
- All tablets should be taken within approximately 5 minutes.
- The tablets may be taken with or without food.
- Subjects will document the timing of investigational product administration on each day of the double-blind treatment via the subject dosing diary.

### **5.5.1. Dose Optimization of Investigational Product**

Each subject is planned to be up-titrated in a double-blind fashion to an optimal dose level of investigational product according to a flexible dose titration scheme. Reaching of the maximum allowed dose level (15 mg, Stage 8) is not mandatory; subjects may achieve a satisfactory clinical response at a lower dose level.

Modifications to the upward titration of investigational product can be made to achieve an optimized dose level. Dose escalation will continue, as tolerated, to a response level judged satisfactory by the investigator. The target dose is the dose at which the individual subject has achieved an optimal clinical balance of motor symptom control and tolerability, based on the judgment of the investigator. The target dose range for PF-06649751 is expected to be between 3 mg to 15 mg once daily.

Dose optimization is to be completed no later than Visit 10; thereafter the achieved dose level will be maintained for the remainder of the double-blind treatment period. Dose adjustments after Visit 10 may be performed only after consultation with the Sponsor Medical Monitor/Study Clinician.

The titration scheme for this study is presented in [Table 2](#).

**Table 2. Titration Scheme of PF-06649751 and Placebo**

Stage # Start Day of Dose Level a,b	PF-06649751 (QD mg)	Placebo
Stage 1/from day 1 a	0.25	P
Stage 2/from day 8 c	0.75	P
Stage 3/from day 15	1.5	P
Stage 4/from day 22	3	P
Stage 5/from day 29	5	P
Stage 6/from day 36	7	P
Stage 7/from day 43	11	P
Stage 8/from day 50	15	P

a. Subjects will initiate the first dose and subsequent dose level increases the day after the corresponding phone/clinic visit (eg, Day 1 is the day after Visit 1).

b. For subjects who will not achieve their individual optimal dose level on the day following Visit 8, dose escalation is permitted, however the final dose level increase must be completed before Visit 10.

c. The increase in dose level from Stage 1 to Stage 2 is a mandatory step at Visit 2 (from Day 8).

#### 5.5.1.1. Dose Optimization Period

- **Stage 1 (Day 1 to Day 7):** Subjects who experience intolerable adverse events during the first week of the study will need to discontinue the investigational product.
- **Stage 2 onward:** Dose level increases are permitted on a weekly basis.

At each planned visit and as necessary at unplanned visits during the Dose Optimization Period, the investigator will evaluate:

- If the current dose level is well tolerated; and
- If the degree of motor symptom control can be considered satisfactory.

Based on this evaluation and investigator discretion, a decision will be made to:

- Decrease the dose to the previous dose level to address potential tolerability findings.
- Stay at the current dose level to address potential tolerability findings, if needed for further clinical stabilization or when the individual subject has achieved an optimal balance of motor symptom control and tolerability.
- Increase the dose to the next higher dose level to evaluate if further clinical benefit can be achieved.

For subjects who have achieved an optimal balance of motor symptom control and tolerability, the investigator should consider an attempt to increase the dose to the next higher dose level in order to evaluate if further clinical benefit can be achieved.

[figure not shown]
Efforts should be made to reach the minimum targeted dose of 3 mg or placebo (Stage 4). Subjects who have not reached Stage 4 by Visit 10 will stay at their current dose for the remainder of the study.

Subjects whose dose had been reduced to the previous dose level and who still do not tolerate the reduced dose level or who do not tolerate a re-challenge at the previously attempted dose level should be returned to the next lower/previous dose level and stay at this dose level for the remainder of the double-blind treatment period.

It is possible that a stable dose can be reached by or before Visit 8. However, continued dose adjustments for efficacy and tolerability may occur until Visit 10.

**Figure 1 (below)** lists the decision flow that should occur at each phone and clinic visit during the Dose Optimization Period:

**Figure 1. Decision Flow**

1. Consider proceeding to the next higher dose level to evaluate if further clinical benefit can be achieved
2. Consider discontinuation if limited tolerability persists

### 5.5.2. Dose Maintenance Period

- The maintenance dose is reached when the individual subject has achieved an optimal balance of motor symptom control and tolerability, based on clinical judgment.
- The target dose range is expected to be 3 mg to 15 mg once daily (Stage 4 – Stage 8). However, a maintenance dose less than 3 mg may be selected, based on tolerability and clinical response.
- Any dose adjustment during the Maintenance Period (after Visit 10) may only be performed after consultation with the Sponsor Medical Monitor/Study Clinician.

### 5.6. Investigational Product Storage

The investigator, or an approved designee, eg, pharmacist, will ensure that all investigational products are stored in a secured area with controlled access under required storage conditions and in accordance with applicable regulatory requirements. An Investigational Product Manual will be supplied to the pharmacy prior to initiation of the study and will provide further information regarding storage conditions of the product.

Investigational product should be stored in its original container and in accordance with the label. Site staff will instruct subjects on the proper storage requirements for take home investigational products, including how to report temperature excursions. See the single reference safety document (SRSD), which for this study is the Investigator's Brochure.

However, storage conditions stated in the single reference safety document (eg, Investigator's Brochure and package insert) will be superseded by the storage conditions stated in the labeling.

Site systems must be capable of measuring and documenting (for example, via a log), at a minimum, daily minimum and maximum temperatures for all site storage locations (as applicable, including frozen, refrigerated and/or room temperature products). This should be captured from the time of investigational product receipt throughout the study. Even for continuous monitoring systems, a log or site procedure that ensures active daily evaluation for excursions should be available. The operation of the temperature monitoring device and storage unit (for example, refrigerator), as applicable, should be regularly inspected to ensure it is maintained in working order.

Any excursions from the product label storage conditions should be reported upon discovery. The site should actively pursue options for returning the product to the storage conditions as described in the labeling, as soon as possible. Deviations from the storage requirements, including any actions taken, must be documented and reported to the sponsor. Once an excursion is identified, the investigational product must be quarantined and not used until the sponsor provides documentation of permission to use the investigational product. It will not be considered a protocol deviation if the sponsor approves the use of the investigational product after the temperature excursion. Use of the investigational product prior to sponsor approval will be considered a protocol deviation.

Specific details regarding information the site should report for each excursion will be provided to the site.

Receipt of materials, door opening and closing, and other routine handling operations where the product(s) are briefly out of the temperature range described in the labeling are not considered excursions.

Site staff will instruct subjects on the proper storage requirements for take home investigational products.

### **5.7. Investigational Product Accountability**

The investigative site must maintain adequate records documenting the receipt, use, loss, or other disposition of the investigational product supplies. Subjects will return Investigational Product to the site per the [Schedule of Activities](#). Additional details regarding the process for accountability will be provided prior to initiation of the study.

#### **5.7.1. Destruction of Investigational Product Supplies**

The sponsor or designee will provide guidance on the destruction of unused investigational product (eg, at the site). If destruction is authorized to take place at the study site, the investigator must ensure that the materials are destroyed in compliance with applicable environmental regulations, institutional policy, and any special instructions provided by Pfizer, and all destruction must be adequately documented.

### **5.8. Concomitant Treatment(s)**

Subjects will abstain from all concomitant medications as outlined in [Appendix 2](#) and [Appendix 3](#), except for the treatment of adverse events.

All concomitant treatments taken during the study must be recorded with indication, daily dose, and start and stop dates of administration. All subjects will be questioned about concomitant treatment at each phone or clinic visit.

Medications taken within 60 days before the first dose of study investigational product will be documented as a prior medication. Medications taken after the first dose of study investigational product will be documented as concomitant medications.

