### 1.5.2. Dose Rationale

PF-06649751 is a potent D1R agonist with terminal half-life long enough to facilitate once-daily dosing. In vitro data suggest CYP3A4 as the primary enzyme responsible for the majority of PF-06649751 metabolism. Data also indicates that overall risk of PF-06649751 to perpetrate drug interactions due to inhibition of P-glycoprotein, breast cancer resistance protein (BCRP), organic cation transporter (OCT1), and/or multidrug and toxin extrusion protein (MATE1) at the 15 mg dose level is low and clinically relevant drug-drug interactions are not anticipated (further information is available in the Investigator Brochure).

Phase 1 studies demonstrate poor tolerability at single oral doses greater than 1.5 mg in healthy subjects and titration improves tolerability at higher doses. The intent of the study is to investigate the safety, tolerability and efficacy in early Parkinson's disease patients. Due to the heterogeneity in disease severity in the patient population, a flexible dosing scheme is being implemented in the study with an aim to get each subject to his/her optimal dose for management of motor symptoms. Such a dosing paradigm would mimic the usage of PF-06649751 in a real-world clinical setting.

Subjects will be titrated to a dose that is deemed optimum by the investigator based on the subject's response with respect to motor control and tolerability. Based on all the PK, safety and tolerability data available to-date, a dose of 15 mg QD is set as the upper limit of daily dose that a subject can achieve in this study. A dose of 3 mg QD is expected to result in average concentrations similar  $C_{eff}$  values established using MPTP monkeys. Based on the observed exposures from study B7601005 (Table 1), a 15 mg QD dose is expected to provide exposures ~1.8 – 4 fold lower than the PK stopping criteria from the 15-week monkey toxicological study. The ~1.8 – 4 fold exposure window provides sufficient margin for a potential increase in PF-06649751 exposures when co-administered with weak inhibitors of CYP3A4. To prevent accidental exposure increases greater than toxicological limits, subjects on moderate or strong CYP3A4 inhibitors will be excluded from the trial until the magnitude of CYP3A4 interaction is defined within a drug-drug interaction study.

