9. Any condition possibly affecting drug absorption, past surgery of the gastrointestinal tract (eg, gastrectomy, colectomy), except cholecystectomy.
10. History of vasculitis.
11. History of Human Immunodeficiency Virus (HIV) infection.
12. History of malignancy other than:

- Non-metastatic basal or squamous cell carcinoma of the skin or carcinoma in situ that was surgically removed in total >1 year before screening and has not recurred.
  - Other type of malignancy which has been in remission 5 years or more before screening and has not recurred.
13. Subjects with first degree family history of unexplained sudden death, or of Long QT syndrome (LQTS).
14. Within 1 year of Screening or between Screening and Visit 1 (Randomization), any of the following: myocardial infarction; moderate or severe congestive heart failure, NYHA class III or IV; hospitalization for, or symptoms of, unstable angina; syncope due to orthostatic hypotension or unexplained syncope; known significant structural heart disease (eg, significant valvular disease, hypertrophic cardiomyopathy); or hospitalization for arrhythmia.

Concomitant Medications:

15. Currently receiving moderate or strong CYP3A4 inducers or CYP3A4 inhibitors (except for topical administration) as outlined in [Section 5.8](#) Concomitant Treatment(s), [Appendix 2](#), and [Appendix 3](#).
16. Currently receiving an antipsychotic, metoclopramide, reserpine, or amphetamine as outlined in [Section 5.8](#) Concomitant Treatment(s) and [Appendix 2](#).
17. Prohibited concomitant medications as outlined in [Section 5.8](#), Concomitant Treatment(s), and [Appendix 2](#).

Screening Assessments:

18. Pregnant female subjects; breastfeeding female subjects; females of childbearing potential (assessed at Screening); male subjects with partners currently pregnant; male subjects able to father children who are unwilling or unable to use a highly effective method of contraception as outlined in this protocol for the duration of the study and for at least 28 days after the last dose of investigational product or longer based upon the compound's half-life characteristics.
19. Screening supine blood pressure  $\geq 160$  mm Hg (systolic) or  $\geq 95$  mm Hg (diastolic), on a single measurement. If abnormal, up to 2 repeats are permitted following at least 5 minutes of rest. The screening value in that case will be the average of the 2 values closest to the normal range.

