### **5.9. Other Prohibited Concomitant Medications**

The following medications will not be permitted within 28 days prior to Visit 1 (Randomization):

- CYP3A4 inducers: the use of moderate and strong inducers of CYP3A4 is not permitted, since they may decrease the levels of the study drug. A list of potential drug inducers is provided in [Appendix 3](#).
- CYP3A4 inhibitors: the use of moderate or strong inhibitors of CYP3A4 is not permitted, since concomitant use these may lead to increased levels of the study drug. A list of potential CYP3A4 inhibitors is provided in [Appendix 3](#).

The use of marijuana is not permitted from Screening through the end of the double blind treatment period.

The following medications will not be permitted within 42 days prior to Visit 1 (Randomization):

- Amphetamines, methylphenidate or other stimulants.
- Antipsychotics, metoclopramide, or reserpine are not permitted.
- Lithium, tricyclic antidepressants, irreversible MAO-A/B inhibitor antidepressants (including moclobemide, tranlycypromine, and phenelzine).
- Antiepileptics are not permitted except if used for chronic painful conditions at steady doses (for example, gabapentin or pregabalin).

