## Appendix 2. Permitted/Prohibited Concomitant Medications

Use Category	Type of Medication	Guidance
Permitted	Any previous, current or new medications for medical illness not listed under the prohibited medication section below.	As needed based on investigator's judgment and subject's medical needs. 
	Hypnotics, sedatives, anxiolytics	Stable low doses of benzodiazepines are permitted. The planned prescription of benzodiazepines for P.r.n. ("as needed") use throughout the study should be discussed with the medical monitor/Pfizer Clinician. For insomnia, non-benzodiazepines are permitted.
	Anticholinergics	Permitted if at a stable dose for at least 42 days prior to Visit 1 (Randomization). No dose changes should be anticipated for the duration of the study.
	MAO-B inhibitors (Parkinson's disease medication)	Permitted if at a stable dose for at least 42 days prior to Visit 1 (Randomization). No dose changes should be anticipated for the duration of the study.
	Amantadine	Permitted if at a stable dose for at least 42 days prior to Visit 1 (Randomization). No dose changes should be anticipated for the duration of the study.
Prohibited	L-Dopa and dopamine receptor agonist medications including pramipexole, ropinirole, rotigotine and apomorphine	Prohibited if prior exposure or history of treatment with dopaminergic agents for more than 28 days and within at least 7 days prior to Visit 1 (Randomization) and throughout the study.
	Amphetamines, methylphenidate or other stimulants	Prohibited at least 42 days prior to Visit 1 (Randomization),
	Antipsychotics or neuroleptics	Antipsychotics, metoclopramide, or reserpine are prohibited at least 42 days prior to Visit 1 (Randomization).
	Antiepileptics	Antiepileptics are prohibited at least 42 days prior to Visit 1 (Randomization), except if used for chronic painful conditions at steady doses (for example, gabapentin or pregabalin).
	Lithium, irreversible MAO-A/B inhibitor antidepressants (including moclobemide, tranylcypromine, and phenelzine)	Prohibited at least 42 days prior to Visit 1 (Randomization). Stable low dose opioids for chronic painful medical conditions may be permitted based on a consultation with the medical monitor.
	Moderate or Strong CYP3A Inhibitors and Inducers	Prohibited at least 28 days prior to Visit 1 (Randomization). Drugs that induce or inhibit the hepatic metabolizing cytochrome 3A4 enzymes.

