	Marijuana	Prohibited from Screening through the end of the double blind treatment period.
	Herbal Supplements	Herbal supplements must be discontinued at least 28 days period to Visit 1 (Randomization). However, Melatonin is permitted if at a stable dose for at least 42 days prior to Visit 1 (Randomization).

1. Investigator to discuss with sponsor as needed.

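### The adverse-event exception in Protocol 5.8 has no carve-out for moderate or strong CYP3A4 inhibitors during dosing, and tricyclics are handled inconsistently

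*Protocol*

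**What the plan says.** **CYP3A4 inhibitors**

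- Protocol 5.8 sets the general on-study rule. Subjects abstain from the drugs in Appendices 2 and 3, "except for the treatment of adverse events". No drug class is held back from the exception. The same section classes anything taken after the first dose as concomitant.
- Protocol 5.9 introduces the CYP3A4 bullets with "The following medications will not be permitted within 28 days prior to Visit 1 (Randomization"). The reason given for the inhibitor bullet is "since concomitant use these may lead to increased levels of the study drug".
- The CYP3A row of Appendix 2 repeats the window: "Prohibited at least 28 days prior to Visit 1 (Randomization"). Appendix 3 lists the drugs and gives no time window.
- Exclusion 15 in 4.2 reads "Currently receiving moderate or strong CYP3A4 inducers or CYP3A4 inhibitors (except for topical administration").
- Section 1.5.2 gives the purpose: "To prevent accidental exposure increases greater than toxicological limits, subjects on moderate or strong CYP3A4 inhibitors will be excluded from the trial". It says the exposure margin is enough for weak inhibitors and makes no such claim for stronger ones.
- Appendix 2 states an on-treatment period for two other classes. Dopaminergic agents are barred "within at least 7 days prior to Visit 1 (Randomization) and throughout the study", and marijuana is "Prohibited from Screening through the end of the double blind treatment period". Section 4.4.1 bars grapefruit until double-blind dosing ends.
- Sections 1.5.3 and 5.9.1 allow anti-emetics for nausea and vomiting. Aprepitant is among the Appendix 3 inhibitors.

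**Tricyclics**

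- Section 5.9 names tricyclic antidepressants among the drugs not permitted in the 42 days before Visit 1.
- Section 5.9.1 permits stable antidepressants and carves out only irreversible MAO-A/B inhibitors.
- The matching prohibited row in Appendix 2 lists lithium and those MAO inhibitors but not tricyclics. The first permitted row of Appendix 2 admits any drug for a medical illness that is not listed as prohibited.

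**The concern.** Section 1.5.2 presents the bar on moderate and strong inhibitors as a safety control. CYP3A4 is thought to do most of the drug's metabolism, the interaction has not been measured, and the bar is to stay until it has been. A control of that kind needs to hold while subjects are taking the drug, above all at the top doses.

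The exception in 5.8 is wide. Section 8.3 defines an adverse event as any untoward medical occurrence, so most new illness during 15 weeks of treatment would qualify. A respiratory infection, a fungal infection or drug-related nausea could each lead to an Appendix 3 inhibitor. The text would not then require the site to call the medical monitor or interrupt dosing. Other classes are treated more strictly: low-dose opioids need a consultation, and planned as-needed benzodiazepines should be discussed with the monitor.

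The tricyclic conflict concerns eligibility and consistency between sites. Two sites could reach opposite answers for the same subject, depending on which section they consult.

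**Working it through.** **Step 1. Does any provision limit the 5.8 exception?**

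| Provision | When it acts | Limits treatment of an adverse event on study? |
|---|---|---|
| 5.8 with Appendix 3 | On study | No, such treatment is excepted |
| 5.9, CYP3A4 bullets | 28 days before Visit 1 | No, although the stated reason shows an on-treatment ban was meant |
| Appendix 2, CYP3A row | 28 days before Visit 1 | No |
| Exclusion 15 | At entry | No |
| 4.4.1, grapefruit | To the end of double-blind dosing | Grapefruit and related citrus only |

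Use for a reason other than an adverse event is barred by the first row. Use for an adverse event is not barred by any row.

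**Step 2. Reproduce the stated margins.** Section 1.3.3 gives unbound exposure at the 15-week monkey NOAEL as Cmax 78.3 ng/mL and AUC 684 ng·h/mL. For humans at 15 mg it gives 19.8 ng/mL and 370 ng·h/mL.

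- Cmax margin: 78.3/19.8 = 3.95 (stated as 4.0)
- AUC margin: 684/370 = 1.85 (stated as 1.8)

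Section 1.5.2 describes the same 1.8 to 4-fold range as the distance to the PK stopping criteria from that study.

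**Step 3. AUC rise that takes mean exposure to the NOAEL, by dose.** Formula: 684 / (370 × dose/15). This assumes dose proportionality, which 1.4.3 reports as roughly true from 5 to 15 mg.

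- 15 mg: 684/370 = 1.85-fold
- 11 mg: 684/271.3 = 2.52-fold
- 7 mg: 684/172.7 = 3.96-fold
- 3 mg: 684/74 = 9.24-fold

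Check against an observed value: the unbound fraction is 370/5993 = 0.0617. The Table 1 AUC at 5 mg then gives 684/(2105 × 0.0617) = 5.26-fold, against 684/(370 × 5/15) = 5.55-fold by scaling. The scaling is adequate for this purpose.

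**Step 4. Margin left for an assumed interaction.** The documents give no interaction size, so the rises below are assumptions. Each entry is the starting margin divided by the rise.

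| Assumed rise | AUC margin, 15 mg | AUC margin, 11 mg | Cmax margin, 15 mg |
|---|---|---|---|
| 1.5-fold | 1.23 | 1.68 | 2.64 |
| 2-fold | 0.92 | 1.26 | 1.98 |
| 3-fold | 0.62 | 0.84 | 1.32 |
| 5-fold | 0.37 | 0.50 | 0.79 |

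The AUC margin falls below 1 between a 1.5- and 2-fold rise at 15 mg, and between a 2- and 3-fold rise at 11 mg.

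**Step 5. Tricyclics.** No arithmetic applies. Section 5.9 prohibits the class by name. Section 5.9.1 admits it as an antidepressant outside the single carve-out, and Appendix 2 admits it by omission together with its general permitted row.

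**The case against.** The strongest reply is that an on-treatment ban already exists. Section 5.8 tells subjects to abstain from Appendix 3 drugs, Appendix 3 has no window, and 5.9 gives concomitant use as its reason. This stands. A reader might infer from the 28-day windows that inhibitors are unrestricted after randomization, and the documents do not support that. Most prohibited rows in Appendix 2, including stimulants and antipsychotics, also give only an interval before Visit 1. The natural reading is that these are washout lengths and that 5.8 carries the on-study rule. The gap is confined to the exception for adverse events.

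A second reply is that the margins overstate the risk. The NOAEL comes from 15 weeks of daily dosing, and passing a NOAEL is not itself toxicity. With a half-life of 21 to 22 hours, a short course of an inhibitor need not produce the full steady-state rise. No frequency is known for a subject at 11 or 15 mg who has an adverse event and is given an Appendix 3 drug. Section 1.4.2 also concludes that doses up to 25 mg were safe and well tolerated. All of this limits the claim. However, the Table 1 AUC at 25 mg (7182, n=7) is only 7182/5993 = 1.20 times the 15 mg value, so it does not cover a 1.85-fold rise.

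Third, medication is queried at every visit, ECGs and vital signs are taken at clinic visits, the dose can be reduced, and a data monitoring committee reviews unblinded safety data. These detect or soften a problem but do not prevent the co-prescription.

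Fourth, 5.9.1 ends in redacted text just after its interaction caution. The finding therefore speaks only for the visible text.

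On tricyclics, the specific ban in 5.9 can be read as overriding the general permission in 5.9.1, and sponsor screening verification may review concomitant medication. Both reduce the practical effect. Neither removes the conflict in the text.

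**Conclusion.** The point holds in a limited form. The text of 5.8 permits a moderate or strong CYP3A4 inhibitor to be added for an adverse event while dosing continues, and no visible provision limits this. That runs against the purpose stated in 1.5.2. It matters mainly at 11 and 15 mg, where AUC rises of about 2.5-fold and 1.85-fold take mean exposure to the monkey NOAEL. At 3 to 7 mg the room is 4.0 to 9.2-fold. The 15 mg figure follows directly from 1.3.3, and the others rest on dose proportionality. Whether a given inhibitor would reach these values cannot be settled from the documents.

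The documents do not show that harm is expected, how often the situation would arise, or that efficacy, power or error rates are affected. None of these is claimed. The tricyclic conflict is real but smaller: it is an inconsistency about who may enter and what they may take, with no safety or efficacy consequence shown.

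**What to change.** - **Section 5.8:** state that the adverse-event exception does not cover Appendix 3 moderate or strong CYP3A4 inhibitors, including those used as anti-emetics, unless investigational product is interrupted or stopped after contact with the medical monitor.
- **Section 5.9 and the CYP3A row of Appendix 2:** extend the window so that it runs from 28 days before Visit 1 to the end of double-blind treatment.
- **Tricyclics:** add them to the prohibited row of Appendix 2 that holds lithium and the MAO inhibitors, and to the carve-out in 5.9.1.

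These are wording changes in a protocol amendment, with no new procedures and no change to sample size or analysis. The cost is an occasional dose interruption or choice of another drug. Necessary treatment of an adverse event remains possible.
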